13.1.2 Exposure Adjusted Incidence Rate

Since the number and percentage of subjects with adverse events might be influenced by differential discontinuation rates in the treatment arms, in addition to the frequency tables above, the exposure adjusted incidence rate EAIR (per 100 patient years at risk) and the cumulative incidence at 6 months, 12, 18 months & 24 months with the 95% confidence interval, using Greenwood's formula, will be reported by treatment arm (pooled roxadustat and pooled placebo) for each of the following event types of special interest: serious TEAEs, renal SAEs, dialysis, deaths, Investigator-determined related serious TEAEs, AEs leading to discontinuation of study drug, TEAE that are severe and/or NCI CTC Grades 3 or higher.

The exposure adjusted incidence rate (per 100 patient years at risk) will be calculated as follows:

$$\frac{\text{Number of subjects with event}}{\text{Total cumulative time at risk (years)}} \times 100$$

Where Total cumulative time at risk is the sum of individual time at risk.

The Time at Risk for a subject with the event of interest will be calculated (in years) as:

$$(\text{First event date} - \text{analysis Date of first dose} + 1) / 365.25$$

Where 'Analysis Date of first dose' is defined as the date of initial dose of the study drug.

The Time at Risk for a subject without the event of interest is calculated as

$$(\text{Last day of contact} - \text{Date of first dose} + 1) / 365.25$$

Risk of each of the TEAE categories of special interest above will be compared (pooled roxadustat vs. pooled placebo) using Cox Regression model. Hazard ratio and its 95% will be calculated for the frequency of pooled roxadustat as relative to pooled placebo for each of the TEAE categories of special interest.

A dot-and-forest plot will be produced showing the above TEAE categories in the y-axis and the incidence rates (pooled roxadustat and pooled placebo), the Cox proportional hazard ratio (pooled roxadustat vs. pooled placebo) and its 95% CI in the x-axis. The system organ classes in the y-axis will be sorted by the hazard ratio.

In addition, cumulative incidence plots for subjects experiencing each of the TEAE categories above will be produced by treatment arm and combined group (pooled roxadustat and pooled placebo). Temporal profile of TEAEs of special interest may also be plotted by combined treatment group (pooled roxadustat vs. pooled placebo) showing the subjects in the y-axis and time to these TEAEs in the x-axis (Appendix 7).

Due to suspected differential dropout rates between roxadustat vs. placebo and the resulted biases on event rates, selected TEAEs and TESAEs will be summarized by PEY censoring for start of chronic dialysis or renal transplant, and also stratified by baseline eGFR category (<10, 10-<15, 15-<30, and ≥ 30 mL/min/1.73m²).

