13.1.1 Proportion of Subjects with TEAE

An AE (classified by preferred term) occurring after the first dose of study medication and up to 28 days after the last dose of study medication will be considered a treatment emergent adverse event (TEAE) if it was not present prior to the first dose of study medication, or it was present prior to the first dose of study medication but increased in severity during the double-blind treatment period. An AE that occurs more than 28 days after the last dose of study medication will not be counted as a TEAE. TEAEs up to 3 days and 7 days after the last dose of study medication may also be evaluated.

The number and percentage of subjects reporting TEAEs in each treatment group will be tabulated by system organ class and preferred term; by system organ class, preferred term, and severity (≥ 3 in a separate table); and by system organ class, preferred term, and Investigator-determined relationship (at least possibly related in a separate table) to study medication. If more than one event occurs with the same preferred term for the same patient, the patient will be counted only once for that preferred term using the most severe and most related occurrence for the summarization by severity and by relationship to the study medication.

The distribution of TEAEs by severity and relationship to study medication will be summarized by treatment group.

The number and percentage of subjects reporting common ($\geq 5\%$ of subjects in any treatment group) TEAEs, treatment-emergent serious AEs (TESAE), renal TESAEs and AEs leading to discontinuation of study medication will be summarized by SOC, preferred term and treatment group, sorted in decreasing frequency overall. In addition, the number and percentage of death and fatal SAEs (i.e., events that caused death) will be summarized by treatment group, SOC and preferred term.

Sensitivity analysis of TEAE during study medication treatment will consist of a summary of TEAE and TESAEs reported after the first dose of study medication up until 72 hours (to cover > 4 half-lives of roxadustat post treatment) and 7 days after the last dose of study medication.

Treatment emergent major cardiovascular events (death, stroke, myocardial infarction) stratified by baseline eGFR (<10 , $10-<15$, $15-<30$, and ≥ 30 mL/min/1.73 m²) will be tabulated.

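### SAP 13.1.2 implies one minus Kaplan-Meier for the cumulative incidence of dialysis and renal SAEs, which overstates the risk of events that death can pre-empt

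*SAP*

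**What the plan says.** SAP section 13.1.2 adds two things to the simple adverse event percentages: an exposure-adjusted incidence rate (EAIR), and "the cumulative incidence at 6 months, 12, 18 months & 24 months with the 95% confidence interval". The sentence continues "using Greenwood's formula, will be reported by treatment arm (pooled roxadustat and pooled placebo"), so a single method serves every listed event type. The list begins "serious TEAEs, renal SAEs, dialysis, deaths, Investigator-determined related serious TEAEs, AEs leading to discontinuation of study drug" and ends with TEAEs that are severe or of CTC Grade 3 or higher. Later in the section, "cumulative incidence plots for subjects experiencing each of the TEAE categories above will be produced by treatment arm".

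The follow-up rule in the section is written for the EAIR. "The Time at Risk for a subject without the event of interest is calculated as" the interval from first dose to the last day of contact. No separate rule is given for a subject whose last contact is death. Risk between arms "will be compared (pooled roxadustat vs. pooled placebo) using Cox Regression model".

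The section recognises that dropout may differ between arms. Its remedy is that "selected TEAEs and TESAEs will be summarized by PEY censoring for start of chronic dialysis or renal transplant", with a further breakdown by baseline eGFR. That remedy does not deal with death.

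**The concern.** Greenwood's formula is best known as the variance of the Kaplan-Meier estimator. If dialysis is estimated by Kaplan-Meier and a subject who dies first is censored, the method treats that subject as someone who could still have started dialysis later. One minus Kaplan-Meier then estimates the risk in a hypothetical setting without death. Cumulative incidence, the quantity the SAP names, is the proportion of subjects who actually have the event by a given time. When some subjects die before the event, the first quantity is larger than the second, and the gap widens with follow-up.

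The later time points are therefore the most exposed. Treatment may run up to 3 years after the last randomization (SAP section 3), so 24-month estimates can be expected. If mortality differs between arms, the gap also differs between arms, and a side-by-side reading of the two percentages is slightly distorted. At stake are the descriptive safety percentages, their confidence intervals and the plots.

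**Working it through.** **Inputs.** From SAP 13.1.2: the time points (6, 12, 18 and 24 months), the variance formula, the event list and the last-contact rule. The documents give no expected rate of dialysis, renal SAE or death, so there is no planned figure to reproduce. Every hazard below is an assumption, held constant over time.

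**Formulas.** With event hazard *a*, death hazard *b* (per year) and time *t* (years):

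- One minus Kaplan-Meier, deaths censored: 1 − exp(−*a t*)
- Cumulative incidence, the target of Aalen-Johansen: *a*/(*a*+*b*) × [1 − exp(−(*a*+*b*) *t*)]

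**Worked case.** Take *a* = 0.25, *b* = 0.08, *t* = 2. The first is 1 − exp(−0.50) = 39.3%. The second is 0.25/0.33 × [1 − exp(−0.66)] = 36.6%. The excess is 2.7 points.

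**Four assumed pairs.** Excess of one minus Kaplan-Meier, in percentage points:

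| *a* | *b* | 6 months | 12 months | 24 months | Values at 24 months |
|---|---|---|---|---|---|
| 0.15 | 0.08 | 0.1 | 0.5 | 1.9 | 25.9% vs 24.1% |
| 0.25 | 0.08 | 0.2 | 0.8 | 2.7 | 39.3% vs 36.6% |
| 0.25 | 0.12 | 0.3 | 1.2 | 4.0 | 39.3% vs 35.3% |
| 0.35 | 0.10 | 0.4 | 1.4 | 4.2 | 50.3% vs 46.2% |

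Over a wider grid (event 0.05-0.30, death 0.03-0.15 per year) the excess is 0.1-1.8 points at 12 months and 0.3-5.6 points at 24 months.

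**Between arms.** Give both arms an event hazard of 0.25, with death hazards of 0.08 and 0.12. One minus Kaplan-Meier is 39.3% in both arms at 24 months. The cumulative incidences are 36.6% and 35.3%, so a difference of about 1.3 points is hidden.

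**Against sampling error.** A simulation used 800 subjects, event hazard 0.20, death hazard 0.10, independent censoring at 0.25 per year and 1000 runs. At 24 months, mean one minus Kaplan-Meier was 32.9% against 30.0% for Aalen-Johansen, with a mean Greenwood standard error of 2.0 points. The excess of 2.9 points is larger than one standard error at the maximum size of the roxadustat arm. For 400 placebo subjects at the same rates, the standard error would be about 2.0 × √2 = 2.8 points, close to the excess.

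**Which categories.** Protocol section 10.2.2 makes death a criterion for an SAE, and section 10.3.3 makes Grade 5 a death.

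- Dialysis and non-fatal renal SAEs: death from another cause pre-empts the event, so the point applies in full.
- Related serious TEAEs and AEs leading to discontinuation: some deaths will count as events and others will pre-empt them, so it applies in part.
- Serious TEAEs and Grade 3+ TEAEs: a treatment-emergent fatal event is itself an event, so it applies little.
- Deaths: it does not apply.

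**The case against.** **The estimator is inferred.** Section 13.1.2 contains neither the words Kaplan-Meier nor a statement that deaths are censored. Elsewhere (SAP 12.3 items 6 and 9, and 12.4) the SAP names Kaplan-Meier when it means it, and Aalen-Johansen also has a Greenwood-type variance. This stands: the method is implied, not stated. It remains the ordinary reading, because one formula covers deaths and dialysis alike and no competing-risk method appears in either document.

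**The net error may not be upward.** A reader might infer that all the reported percentages are too high in both arms. The documents do not support that. Under SAP 13.1.1, "An AE that occurs more than 28 days after the last dose of study medication will not be counted as a TEAE", while time at risk for event-free subjects runs to last contact, and discontinued subjects are followed until the study ends (protocol 5.3 and 7.1.2.6). If that time feeds the curve, TEAE-limited estimates are pulled down. With assumed hazards of 0.20 (event), 0.10 (death) and 0.25 (discontinuation), Kaplan-Meier at 24 months falls to 26.9%, against a cumulative incidence of 30.1% had every subject stayed on treatment. This stands as a limit on direction. It is a separate problem and does not make censoring at death correct.

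**The consequence is small.** A reader might also infer that the programme's main cardiovascular safety conclusion is affected. That conclusion rests on pooled adjudicated events under a separate SAP (protocol 8.4, SAP 13.1.4), not on these percentages. No decision rule uses them, and the Cox comparison is valid as a cause-specific hazard ratio.

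**Death is not ignored.** Deaths are reported in the same analysis, and SAP 4.3 has composites of renal replacement therapy or death. These help interpretation but do not correct the dialysis or renal SAE percentages. The IPCW method in Appendix 8 is called for only by the rescue and transfusion endpoints.

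**Conclusion.** The point holds in limited form and is minor. On its ordinary reading, SAP 13.1.2 estimates the risk of dialysis and renal SAEs with subjects who die first censored, and that choice alone overstates their cumulative incidence. The upward direction of this component is certain whenever deaths precede the event. The net error in TEAE-limited categories is not established.

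The size depends on rates that the documents do not give. On the four assumed pairs it is negligible at 6 months (0.1-0.4 points), about 0.5-1.4 points at 12 months and 1.9-4.2 points at 24 months. A death hazard 50% higher in one arm (0.12 against 0.08, event hazard 0.25) distorts the between-arm contrast by about 1.3 points at 24 months. These figures assume constant hazards. The EAIR and the Cox hazard ratios are not made wrong by censoring deaths.

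**What to change.** In SAP 13.1.2:

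- For dialysis and the other categories in which death is not itself an event, estimate the cumulative incidence by Aalen-Johansen with death as a competing event, and use that estimator's own variance for the confidence intervals. For dialysis, treat kidney transplant as a competing event too.
- In categories that include fatal events, count those deaths as events. Say for each category which deaths count and which compete.
- Use the same estimator for the cumulative incidence plots.
- Keep Kaplan-Meier with Greenwood for deaths.
- State the censoring date for each event type. This also settles whether time more than 28 days after last dose enters the TEAE-limited curves.
- Leave the EAIR and the cause-specific Cox hazard ratios as they are.

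The cost is a short SAP edit, best made before unblinding, and a change of estimator in programming. No new data are needed and no hypothesis test changes. The stated risks in the affected categories become slightly lower.

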9.4.4.1 Adverse Events

Adverse events will be coded using Medical Dictionary for Regulatory Activities (MedDRA).

An AE (classified by preferred term) occurring during the double-blind treatment period will be considered a treatment emergent adverse event (TEAE) if it was not present prior to the first dose of study medication, or it was present prior to the first dose of study medication but increased in severity during the double-blind treatment period. An AE that occurs more than 28 days after the last dose of study medication will not be counted as a TEAE.

The number and percentage of subjects reporting TEAEs in each treatment group will be tabulated by system organ class (SOC) and preferred term; by SOC, preferred term, and severity; and by SOC, preferred term, and relationship. If more than one event occurs with the same preferred term for the same subject, the subject will be counted only once for that preferred term

using the most severe and most related occurrence for the summarization by severity and by relationship to the study medication.

The overall distribution of TEAEs by severity and relationship to study medication will be summarized by treatment group.

The number and percentage of subjects reporting common ($\geq 5\%$ of subjects in any treatment group) TEAEs, Treatment-Emergent serious AEs (TESAE), fatal SAEs (ie, events that caused death), and AEs leading to discontinuation of study medication will be summarized by SOC, preferred term and treatment group, sorted in decreasing frequency overall

Treatment emergent adverse events will also be reported in terms of incidence rate per PEY.

Listings will be presented of subjects with SAEs, subjects with AEs leading to discontinuation, and subjects who died.

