10 STUDY MEDICATION

10.1 EXTENT OF EXPOSURE

Exposure to study medication will be summarized in terms of treatment duration, which is calculated as the number of days from the date of first double-blind medication taken to the date of last dose taken, inclusively.

Total weekly study drug exposure is defined as the total prescribed dose (in mg or mg/kg) of study drug administered within the week (per CRF dosing week).

Duration of exposure, weekly exposure and total study drug exposure will be tabulated by treatment group and overall for the safety population.

Per dose amount and dosing frequency for every four-week period will also be tabulated by treatment group for the Safety population.

Patient-Exposure-Year (PEY) is defined as $(\text{Last Dose Date} - \text{First Dose Date} + 1)/365.25$.

Patient-Followup-Year (PFY) is defined as $(\text{Last Dose Date} - \text{First Dose Date} + 28)/365.25$.

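### TEAE and TESAE rates per patient-exposure-year count events for 28 days after the last dose, but the denominator stops at the last dose

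*SAP*

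**What the plan says.** - **Events counted.** SAP 13.1.1 takes as treatment-emergent an event "occurring after the first dose of study medication and up to 28 days after the last dose of study medication", subject to the usual new-or-worsened condition. It closes the window explicitly: "An AE that occurs more than 28 days after the last dose of study medication will not be counted as a TEAE".
- **Time counted.** SAP 10.1 defines PEY as last dose date minus first dose date plus 1, over 365.25. No time after the last dose enters.
- **Where the two meet.** The last paragraph of SAP 13.1.2 begins "Due to suspected differential dropout rates between roxadustat vs. placebo and the resulted biases on event rates" and continues that "selected TEAEs and TESAEs will be summarized by PEY censoring for start of chronic dialysis or renal transplant", with a further breakdown by baseline eGFR category. Protocol 9.4.4.1 adds: "Treatment emergent adverse events will also be reported in terms of incidence rate per PEY".
- **A second denominator.** SAP 10.1 also has a follow-up year: "Patient-Followup-Year (PFY) is defined as" last dose minus first dose plus 28, over 365.25. No analysis in the SAP text uses it. Table specifications are in a separate document (SAP 1), so this statement covers the SAP text only.
- **A different rate.** SAP 13.1.2 also specifies an EAIR. Its time at risk runs from first dose to the first event or, without an event, to the last day of contact. It does not use PEY.

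**The concern.** For each subject followed after stopping, up to 28 days of events enter the numerator with no matching time in the denominator. The excess is a fixed number of days, so it weighs more when exposure is short. If mean exposure differs between arms, the two rates are inflated by different amounts and their ratio moves away from 1 even when the true rates are equal. The SAP introduces the PEY summaries because it expects unequal dropout, which is the setting in which this happens. Low-eGFR strata would be affected most if their exposure is short. At stake is the between-arm reading of descriptive safety rates in this study.

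**Working it through.** The documents state no adverse-event rate, mean exposure or dropout figure, so there is no planned figure to reproduce.

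**Inputs.** The post-dose window is 28 days (SAP 13.1.1), so w = 28/365.25 = 0.0767 years. The PEY denominator ends at the last dose (SAP 10.1). Mean exposure T per arm is assumed to lie between 0.5 and 2 years; SAP 3 makes treatment duration variable, from possibly under 52 weeks up to 3 years after the last randomization.

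**Step 1: inflation within an arm.** With constant event rate r, expected events per subject are r(T + w) and PEY per subject is T. The reported rate is r(T + w)/T, so inflation = 1 + w/T. This is exact for event counts. For counts of subjects with an event it is close when events are uncommon. The documents do not say which is meant.

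| Mean exposure T (years) | Inflation of rate per PEY |
|---|---|
| 0.5 | 15.3% |
| 0.75 | 10.2% |
| 1.0 | 7.7% |
| 1.25 | 6.1% |
| 1.5 | 5.1% |
| 2.0 | 3.8% |

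**Step 2: effect on the ratio.** With equal true rates, the apparent ratio of the longer-treated (L) to the shorter-treated (S) arm is (1 + w/T_L)/(1 + w/T_S).

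| T_S vs T_L (years) | Apparent ratio |
|---|---|
| 0.5 vs 1.0 | 1.0767/1.1533 = 0.93 |
| 0.75 vs 1.25 | 1.0613/1.1022 = 0.963 |
| 1.0 vs 2.0 | 1.0383/1.0767 = 0.964 |
| 1.0 vs 1.5 | 1.0511/1.0767 = 0.976 |
| 1.0 vs 1.25 | 1.0613/1.0767 = 0.986 |
| 1.5 vs 2.0 | 1.0383/1.0511 = 0.988 |

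Equal exposure gives 1.000.

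**Step 3: an example in counts.** Assume a true rate of 30 per 100 years. An arm of 400 with mean exposure 1.0 year has 120 on-treatment and 9.2 post-dose events over 400 PEY: 129.2/400 = 32.3 per 100 PEY. An arm of 800 with mean 1.5 years has 360 + 18.4 events over 1,200 PEY: 378.4/1,200 = 31.5 per 100 PEY. The ratio is 0.976.

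**Step 4: simulation.** Two million subjects per arm were simulated with the same true rate, exponential discontinuation and a 2-year cap, giving mean exposures of about 1.0 and 1.5 years. The ratio per PEY was 0.977 (formula 0.976). With the 28 days added to the denominator it was 1.001.

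**Step 5: subjects without a post-dose window.** Let f be the share of an arm whose observation ends at or before the last dose, for example because dialysis censoring on treatment cuts off both events and time. Inflation becomes 1 + (1 − f)w/T. With T_S = 1.0, T_L = 1.5 and f = 0 in the longer arm:

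| f in shorter arm | 0 | 0.1 | 0.2 | 0.3 | 0.4 | 0.5 |
|---|---|---|---|---|---|---|
| Apparent ratio | 0.976 | 0.983 | 0.990 | 0.998 | 1.005 | 1.012 |

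The bias vanishes at f = 1 − T_S/T_L = 1 − 1/1.5 = 1/3 and reverses slightly above that.

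**Step 6: is the SAP's follow-up year the matching denominator?** Not quite. PEY counts T days inclusively (the +1), so an inclusive count to 28 days after the last dose is last dose − first dose + 29. The SAP's +28 is one day short, leaving 0.5% inflation at 0.5 years and 0.2% at 1.5 years. It is also unconditional: every subject is credited with the extra time, whether observed or not.

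**The case against.** **The reach is narrow.** The SAP's specified between-arm comparison of serious, related serious, severe and fatal events and of events leading to discontinuation is the EAIR with Cox hazard ratios. Neither uses PEY. The PEY summary covers selected events, with no test or ratio specified. This stands, and the point is limited to the PEY rates. A reader might infer that all adverse-event rates in the plan are affected; the EAIR definition rules that out.

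**The direction is not fixed.** The quoted summary censors at chronic dialysis or transplant, and step 5 shows that this can cancel or slightly reverse the bias. This stands for that summary. Protocol 9.4.4.1 states no such censoring. A reader might also infer that the mismatch makes roxadustat look safer. That requires placebo to stop earlier. More early stopping on placebo is plausible, since Protocol 4.6.2.2 withdraws subjects at a third ESA course and Protocol 9.1 assumes response rates of 65% vs 25%, but neither document says which arm will stop first.

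**The effect might seem larger if events cluster after stopping.** If the event rate doubled or tripled in the 28 days, the 52- vs 26-week ratio per PEY would be 0.882 or 0.842. But with a matched 28-day denominator it would still be [(364 + 56)/392]/[(182 + 56)/210] = 0.945, or [(364 + 84)/392]/[(182 + 84)/210] = 0.902. The mismatch contributes 0.882/0.945 = 0.842/0.902 = 0.933 in both cases, as at a constant rate. The remainder is clustering, which a matched denominator does not remove, and no section supports a doubled or tripled rate.

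**Shorter windows exist.** SAP 13.1.1 has 3- and 7-day windows. On PEY, in the simulated case, they would bring the ratio to 0.997 and 0.994. Nothing in the SAP ties them to the PEY summaries.

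**Conclusion.** The numerator and denominator of the TEAE/TESAE rates per PEY do not cover the same time, on the SAP's own definitions. That is wrong as written and should be corrected. The size is modest: about 5% to 15% on a single arm's rate for mean exposures of 78 down to 26 weeks, and a factor of about 0.93 to 0.99 on the longer-to-shorter rate ratio. Only the 0.5 vs 1.0 year pair reaches the lower end; the other pairs tried give 0.96 to 0.99.

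These figures rest on assumed exposures, a constant and equal event rate, and a full 28-day window for every subject in both arms. Under those conditions the longer-treated arm is favoured. If subjects in the shorter-treated arm lose the window, the bias shrinks or turns; if subjects in the longer-treated arm lose it, for example by moving to the extension study, it grows. The documents support neither a claim that roxadustat is the arm favoured nor a larger effect from events clustering after stopping.

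**What to change.** For the TEAE/TESAE rates now stated per PEY in the last paragraph of SAP 13.1.2 and in Protocol 9.4.4.1 only, replace PEY with observed follow-up from first dose to the earliest of:

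- 28 days after the last dose (counted inclusively: last dose − first dose + 29);
- death;
- last contact or withdrawal;
- rollover to the extension study;
- for the censored summary, start of chronic dialysis or transplant.

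Apply the same cut-off to the events. Do not substitute the follow-up year of SAP 10.1 unchanged: besides being one day short, it would credit time that was never observed.

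Alternatively, keep PEY and count only events up to the last dose.

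Leave the EAIR denominator in SAP 13.1.2 as it is. The cost is some reprogramming of denominators and slightly lower reported rates; no new data are needed.
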